| Key Inclusion/Exclusion Criteria | All Local Authorities (LAs) in England will be eligible to participate. However, we will start recruitment by targeting the 40% most deprived LAs in England. Local authority Key Informants (LAKI) will be eligible if they (a) work at participating LA, and (b) have a core responsibility for food policies. Workshop participants will be eligible if they are attending the intervention workshop and happy to provide consent for participation. |
| Study Type | A single centred, unblinded, parallel-group superiority RCT |

| | |
|-------------------------|--|
| Target Sample Size | 60 LAs, 30 per group |
| Primary Outcome | Number of policies planned or implemented within the last 12 months that explicitly aim to reduce dietary health inequalities (DHI) |
| Key Secondary Outcomes | 
 • Distribution of polices across a scale of potential to achieve system change (Potential of policies) • Perceptions of: 
 ○ Personal and shared local understanding of DHI (Understanding) ○ Personal and shared commitment to address DHI locally (Commitment) ○ Strength of local collaborations to address DHI (Collaboration) ○ Confidence that additional solutions to address DHI locally will be implemented in the next 12 months (Confidence) |
| Intervention duration | 1 workshop plus around 3 pre-meets and 1 post-meet |
| Follow up duration | 12 months |
| Date of first enrolment | TBC |
| Planned Study duration | Three years |

Protocol Signatures

I agree to ensure that the confidential information contained in this document will not be used for any other purpose beyond the evaluation or conduct of the investigation with the prior written consent of the Sponsor.

I also confirm that I will make the findings of the study publicly available through publication or other dissemination tools without any unnecessary delay and that an honest, accurate and transparent account of the study will be given; and that any discrepancies from the study as planned in this protocol will be explained.

Chief Investigator: [name]

Signature:

Date: 02 Feb 2026

Protocol Revision Chronology

| Version | Date | Details |
|---------|------------------|-------------------|
| 1.0 | 02 February 2026 | Original protocol |

Contents

| | |
|---|----|
| List of Abbreviations..... | 6 |
| Trial flow chart/other figures | 7 |
| 1 Introduction | 9 |
| 1.1 Background and rationale | 9 |
| 1.2 The Intervention | 9 |

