1.1 Background and rationale

People living in less affluent circumstances in the UK consume less healthy diets (1) and experience higher levels of diet-related disease. Almost 15% of UK households have recently experienced food insecurity. (2) Dietary health inequalities (DHI) are strongly shaped by the cost (3) and availability (4) of healthier foods and by wider, interacting local, national and international food system processes. (5)

Whilst there are many potential levers to address DHI at national level e.g. food taxes and subsidies, national-level policymaking can be slow. There is little evidence that current approaches are working. (1) Local authorities (LAs) have access to different levers and can act more flexibly than national government, e.g. by working with the community food sector, to provide place-based solutions. In England, local authorities (LAs) play a central role in shaping local environments for health and have access to a range of policy levers that enable flexible, place-based action, often in partnership with community organisations, charities, food system actors and academic institutions.

Systems thinking is “a way of thinking about and analysing things by recognising complexity, patterns and interrelationships rather than focusing on [linear] cause and effect”. (6) One method to support systems thinking is group model building (GMB). (7) GMB uses facilitated, scripted procedures to help stakeholder groups create visual representations of a problem through a systems thinking lens and use this to generate potential solutions. (7) Case-study evidence suggests that GMB can improve shared understanding, cross-sector collaboration and solution generation, but evidence of its impact on implementation is limited. (7, 8) There is a near absence of randomised controlled trial (RCT) evidence evaluating the impacts of GMB. (9) Although GMB has been used to address health and dietary inequalities in settings such as Jersey (10), no RCT has evaluated its effectiveness in supporting English LAs to implement policies aimed at reducing DHI. This study aims to address this evidence gap by adapting and refining an existing GMB intervention and evaluating its impact through an RCT in English local authorities, alongside a process evaluation and documentation of intervention costs.

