1.2 The Intervention

The intervention was co-developed by MW, KP and AS with Jersey’s public health team, then refined and delivered in Guernsey. The Association of Directors of Public Health confirm DHI are a high priority, and the intervention would be attractive.

The intervention will be flexible to local context, is described using the Template for Intervention Description and Replication, (11) is supported by a Theory of Change (**Figure 1**), will be delivered by the research team and comprise:

- 1 or more online 2-hour pre-meet with the key informant (defined below; and relevant team members) ~3 months pre-workshop to review roles, agree upon a focus, and identify workshop participants. Workshop participants (n~15) will be local decision makers in any sector with the power to enact workshop insights (12) and representatives of local community food organisations to bring the voice of those with experience of DHI. Conducting GMB in one day is ambitious but necessary to maintain engagement. Focusing on one locally-agreed population or outcome (e.g.

children, vegetable intake) makes one-day manageable and the intervention flexible to local context. Follow-up meetings will be conducted as required.

- intelligence website circulated to workshop participants summarising local data on DHI to provide context. To be developed by Food Foundation from routinely available data (<https://fingertips.phe.org.uk/>) and their regular food security surveys. Including e.g. local prevalence of children in poverty not eligible for free school meals, type 2 diabetes and food insecurity.
- one-day in-person GMB workshop, developing a CLD and using this to identify potential solutions. Guided by manuals and scripts. Facilitated by 2-3 researchers.
- Around three online 1-2 hour post-meets with key informants (and team) 1 week, 1 month and 3 months post-workshop to refine the CLD, identify further solutions, and support solution prioritisation. Informed by our comprehensive database of Food System Transformation Solutions enabling sharing of best practice.(13)

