1.4 Primary & Secondary outcomes

1.4.1 Primary outcomes

Number of policies planned or implemented within the last 12 months that explicitly aim to reduce DHI

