2.5 Randomised Control Trial Data collection

2.5.1 Local authority level baseline and 12-month data collection for primary outcome

Based on the logic model described in Figure 2, data will be collected from each LA on the primary outcome at baseline and 12 months to document existing policies related to dietary inequalities prior to randomisation and intervention implementation. These data provide a reference point for assessing change at the 12-month follow-up interview. A structured interview guide will be used with a checklist of questions (**Table 1**) to identify policies. All interviews will be recorded on Microsoft Teams. Interviews will be conducted by a member of the research team with the LAKI. The interview recording and generated transcription will be stored until the data capture form has been completed and will then be deleted.

Table 1. Key Informant interview guide for baseline data collection

| Variable | Interview guide |
|----------------------------------|--|
| Date | 1. Date of data collection |
| LA and KI information | 
 1. Name of LA 2. What role does the Key Informant have 3. How long as the Key informant been in their current role? 4. How long has the Key Informant been in a role relevant to dietary inequalities |
| Current food strategies | 
 1. Does the LA have a current Food Strategy (Y/N) 2. Is the LA part of a local food partnership (Y/N) 3. Is the LA a member of the Health Determinants Research Collaboration (Y/N) |
| Current policies for DHI (known) | 1. Can you tell me what policies have been put in place in the last 12 months or will be put in place in the next 12 months to address dietary inequalities (defined as any intentional actions explicitly aiming to address dietary inequalities)? Use relevant prompts with examples from the Food System Transformation Solution Bank |

| | |
|--|---|
| | 
 2. For each policy: what was (or will be) the date of implementation? 3. For each policy: please tell me more about that, what it involves etc Is there anything else that's relevant for this policy? (for each response on a particular policy, ask again about details and repeat until data saturation is achieved for that policy). 4. Are there any other policies in place to address dietary inequalities? Repeat the above questions (i.e., 2-4) for each policy until all policies known to the Key Informant are given. |
|--|---|

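### The primary outcome pools planned with implemented policies and no listed quantitative outcome separates them, so a positive result need not mean more implementation

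*Protocol*

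**What the plan says.** The synopsis gives the primary outcome as "Number of policies planned or implemented within the last 12 months that explicitly aim to reduce dietary health inequalities (DHI", and section 1.4.1 repeats it. Section 3.3 analyses it as one mean per arm, by linear regression adjusted for baseline.

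Section 2.5.1 (Table 1) shows how the count is obtained. The key informant is asked "what policies have been put in place in the last 12 months or will be put in place in the next 12 months", a policy being "defined as any intentional actions explicitly aiming to address dietary inequalities". A follow-up question reads "For each policy: what was (or will be) the date of implementation". Past and future items therefore come from one question, and each carries a date.

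On purpose, section 1.1 says case studies already suggest that group model building helps to generate solutions, while evidence on implementation is limited. It adds that "no RCT has evaluated its effectiveness in supporting English LAs to implement policies aimed at reducing DHI", and that the study aims to fill this gap.

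On the intervention, section 1.2 describes a "one-day in-person GMB workshop, developing a CLD and using this to identify potential solutions". Post-meets with the key informant follow, up to three months after the workshop, to find further solutions and help rank them.

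The secondary outcomes (section 1.4.2) are the policies' potential for system change and four perception measures. None records whether a policy has been implemented. Objective 5 of the process evaluation (section 2.8.2) looks at how far solutions are implemented, but only to aid interpretation and not to assess effectiveness.

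**The concern.** A planned policy and an implemented one each add one to the same total. The person who reports the total knows the allocation (section 3.2 says the local authorities are unblinded) and, in the intervention arm, has worked with the research team on identifying and ranking solutions. A member of the research team conducts the interview.

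The count can therefore rise because informants in the intervention arm name more things that they expect to do, with no difference in what has been done. A positive primary result would then be compatible with better solution generation, which section 1.1 treats as already suggested, and would leave the implementation question open. As the outcomes are listed, no randomised comparison would tell the two explanations apart.

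**Working it through.** **Inputs.** 60 local authorities, 30 per arm; a difference of two policies; SD 3 or SD 2; stated power 72% and 97% (all section 3.1). The protocol gives no significance level, so two-sided 0.05 is assumed. It gives no expected split between planned and implemented policies.

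**Step 1: reproduce the stated power.** Standard error = SD × √(2/30); power ≈ Φ(difference / standard error − 1.96).

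- SD 3: standard error 0.775; 2/0.775 = 2.58; Φ(0.62) = 73.3%. Noncentral t with 58 df: 71.9%.
- SD 2: standard error 0.516; 2/0.516 = 3.87; Φ(1.91) = 97.2%. Noncentral t: 96.8%.

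Both stated figures reproduce. A one-sided 0.05 test would give 82.6% at SD 3, which does not match 72%, so two-sided 0.05 is the setting implied.

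**Step 2: what the test responds to.** The regression sees only the total. If the whole two-policy difference is planned items and the implemented means are equal, the power in step 1 still applies: about 97% at SD 2. As a check on the contrast, 20,000 trials were simulated with assumed Poisson counts: control means of 3 implemented and 1 planned (pooled SD √4 = 2), two extra planned items in the intervention arm, and an unadjusted t-test. The pooled count was significant in 93% of trials and the implemented-only count in 5%.

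**Step 3: whether the SD 3 case counts as success.** Local authorities per arm for 90% power = 2 × (SD/2)² × (1.96 + 1.28)².

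- SD 2: 2 × 1 × 10.51 = 21.0, so 22 per arm, 44 in all.
- SD 3: 2 × 2.25 × 10.51 = 47.3, so 48 per arm, 96 in all.

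Section 3.1 treats a requirement above 60 as underpowered and has the study reported as a pilot. Only the SD 2 illustration therefore describes a trial that would be presented as adequately powered.

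**Step 4: power of an implemented-only count.** The SDs are kept as in the plan, and the share of the two-policy effect implemented in time is assumed (normal approximation).

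| Share implemented | Difference | Power, SD 2 | Power, SD 3 |
|---|---|---|---|
| 100% | 2.0 | 97% | 73% |
| 75% | 1.5 | 83% | 49% |
| 50% | 1.0 | 49% | 25% |
| 25% | 0.5 | 16% | 9% |

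**The case against.** Pooling is a defensible choice. Local policy can take longer than a year, the outcome is openly labelled as planned or implemented, and research question 1 asks only about the listed outcomes. The date of each policy is recorded, and a split by date could appear in a statistical analysis plan that is not shown. The system-change outcome gives some protection against counting trivial items. All of this supports keeping the pooled count as primary. It does not supply a listed outcome for the question that section 1.1 poses, and the list of outcomes belongs to the protocol.

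Three stronger readings are tempting, and the documents do not support them.

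- *The workshop's list of solutions itself counts as success.* It does not. The informant must report an item as something that will be put in place within 12 months, and is asked for its date and details. The outcome is also taken at 12 months, not straight after the workshop. What remains is that this is a stated intention, with no outside confirmation described.
- *Control authorities have no way of generating solutions.* Section 2.8.3 expects them to hold food programme meetings and food poverty action plan workshops, and section 2.3 admits authorities with existing food strategies. They lack only the process that the trial delivers.
- *Every plan should be backed by a formal document.* That would narrow the protocol's broad definition of a policy and could exclude the less formal actions that it admits. It is a debatable trade-off and not needed to repair this point.

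**Conclusion.** The point holds as a gap between the stated purpose and the listed outcomes. There is no error of arithmetic, and the power figures are right. A positive primary result could reflect reported intentions alone, and no quantitative outcome in the protocol would show whether it did.

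The size can only be illustrated. At SD 2, a difference of two policies made up wholly of plans would be detected with about 97% probability. This rests on a two-sided 5% level and on a scenario, two extra plans and no extra implementation, that the documents neither predict nor exclude. A reader might extend it to a 72% chance of a false claim of success at SD 3. Section 3.1 blocks that, because the trial would then be reported as an underpowered pilot.

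**What to change.** Keep the pooled count as the primary outcome and make three additions.

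1. Add to section 1.4.2 and the synopsis a secondary outcome: the number of policies with an implementation date between the baseline and 12-month interviews. Analyse it with the same baseline-adjusted linear regression, taking as baseline value the policies put in place in the 12 months before the baseline interview.
2. Report planned and implemented counts by arm whenever the primary result is reported.
3. State in section 3.3 that any conclusion about implementation rests on the implemented-only count.

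Table 1 is headed as the baseline guide, so the protocol should also say that the date question is asked again at 12 months and entered on the data capture form. Section 2.5.1 has the recording and transcript deleted once that form is complete.

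The cost in data collection is close to nil, since the dates are already asked for. The statistical cost is real: the implemented-only count will be smaller, and its power may be as low as step 4 of the working shows. It should be read with its confidence interval, and a non-significant result should not be taken as evidence of no effect on implementation.

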
 The picture can't be displayed.

Figure 2. CONSORT diagram

1 Introduction

1.1 Background and rationale

People living in less affluent circumstances in the UK consume less healthy diets (1) and experience higher levels of diet-related disease. Almost 15% of UK households have recently experienced food insecurity. (2) Dietary health inequalities (DHI) are strongly shaped by the cost (3) and availability (4) of healthier foods and by wider, interacting local, national and international food system processes. (5)

Whilst there are many potential levers to address DHI at national level e.g. food taxes and subsidies, national-level policymaking can be slow. There is little evidence that current approaches are working. (1) Local authorities (LAs) have access to different levers and can act more flexibly than national government, e.g. by working with the community food sector, to provide place-based solutions. In England, local authorities (LAs) play a central role in shaping local environments for health and have access to a range of policy levers that enable flexible, place-based action, often in partnership with community organisations, charities, food system actors and academic institutions.

Systems thinking is “a way of thinking about and analysing things by recognising complexity, patterns and interrelationships rather than focusing on [linear] cause and effect”. (6) One method to support systems thinking is group model building (GMB). (7) GMB uses facilitated, scripted procedures to help stakeholder groups create visual representations of a problem through a systems thinking lens and use this to generate potential solutions. (7) Case-study evidence suggests that GMB can improve shared understanding, cross-sector collaboration and solution generation, but evidence of its impact on implementation is limited. (7, 8) There is a near absence of randomised controlled trial (RCT) evidence evaluating the impacts of GMB. (9) Although GMB has been used to address health and dietary inequalities in settings such as Jersey (10), no RCT has evaluated its effectiveness in supporting English LAs to implement policies aimed at reducing DHI. This study aims to address this evidence gap by adapting and refining an existing GMB intervention and evaluating its impact through an RCT in English local authorities, alongside a process evaluation and documentation of intervention costs.

1.2 The Intervention

The intervention was co-developed by MW, KP and AS with Jersey’s public health team, then refined and delivered in Guernsey. The Association of Directors of Public Health confirm DHI are a high priority, and the intervention would be attractive.

The intervention will be flexible to local context, is described using the Template for Intervention Description and Replication, (11) is supported by a Theory of Change (**Figure 1**), will be delivered by the research team and comprise:

- 1 or more online 2-hour pre-meet with the key informant (defined below; and relevant team members) ~3 months pre-workshop to review roles, agree upon a focus, and identify workshop participants. Workshop participants (n~15) will be local decision makers in any sector with the power to enact workshop insights (12) and representatives of local community food organisations to bring the voice of those with experience of DHI. Conducting GMB in one day is ambitious but necessary to maintain engagement. Focusing on one locally-agreed population or outcome (e.g.

children, vegetable intake) makes one-day manageable and the intervention flexible to local context. Follow-up meetings will be conducted as required.

- intelligence website circulated to workshop participants summarising local data on DHI to provide context. To be developed by Food Foundation from routinely available data (<https://fingertips.phe.org.uk/>) and their regular food security surveys. Including e.g. local prevalence of children in poverty not eligible for free school meals, type 2 diabetes and food insecurity.
- one-day in-person GMB workshop, developing a CLD and using this to identify potential solutions. Guided by manuals and scripts. Facilitated by 2-3 researchers.
- Around three online 1-2 hour post-meets with key informants (and team) 1 week, 1 month and 3 months post-workshop to refine the CLD, identify further solutions, and support solution prioritisation. Informed by our comprehensive database of Food System Transformation Solutions enabling sharing of best practice.(13)

1.3 Research Questions

1) What is the impact of the intervention on the primary and secondary outcomes listed below?

2) How do local stakeholders understand DHI and their potential solutions, how does this evolve during the course of the intervention?

3) What are the costs of the intervention?

1.4 Primary & Secondary outcomes

1.4.1 Primary outcomes

Number of policies planned or implemented within the last 12 months that explicitly aim to reduce DHI

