2.8.3 Methods

Overview and sample

The qualitative PE will use a qualitative mixed-methods, embedded design. Data collection will occur in approximately 20 purposively sampled local authorities (~10 intervention, ~10 control), representing diverse geographies, organisational structures, and socio-demographic profiles. Within each LA, we will work with the key informants to identify people to interview (intervention and control) based on their role, knowledge, and involvement in DHI-relevant activities and suitable workshops/meetings to observe (control LAs only).

In each of the ~10 intervention PE sites activities will include:

- Intervention workshop **observations**
- post workshop **semi-structured interviews** with the key informant and one other workshop attendee
- 6-12 month post workshop follow-up semi-structured interviews with the same two participants (i.e key informant and one other meeting attendee)

In each of the ~10 control PE sites, we will identify and recruit interview participants in collaboration with the LAKI and work with them to select and negotiate access to relevant team meetings or planning events they are involved in that could serve as a comparable control to the intervention workshops. This will include gatherings like holiday hunger working group meetings, food programme meetings, and food poverty action plan workshops. We will then observe these meetings / events and interview around two attendees (LAKI plus one other) using the same data collection tools and approaches as we are using for the intervention workshops, so that they can be compared. This will help us distinguish between features, outcomes and perceived effects that are either (i) inherent to some collaborative team-based approaches to addressing dietary health inequalities or (ii) particular to the intervention workshop.

Workshop observations

Intervention LAs (≈10) and Control LAs (≈10):

- Structured observations of intervention workshops using a semi-structured pro forma.
- Unstructured fieldnotes documenting emerging reflections, unexpected observations, and contextual insights.

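### The primary count depends on what one informant sees as aimed at dietary inequalities, a view that the intervention is meant to change in one arm only

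*Protocol*

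**What the plan says.** The primary outcome (Protocol section 1.4.1) is "Number of policies planned or implemented within the last 12 months that explicitly aim to reduce DHI". The count comes from a structured interview at baseline and at 12 months (section 2.5.1): "Interviews will be conducted by a member of the research team with the LAKI". There is one such informant per LA.

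The filter sits in the wording of Table 1, question 1, where a qualifying policy is "defined as any intentional actions explicitly aiming to address dietary inequalities". The interviewer may prompt with examples from the Food System Transformation Solution Bank. Question 2 then asks "For each policy: what was (or will be) the date of implementation", question 3 asks what each policy involves, and question 4 asks "Are there any other policies in place to address dietary inequalities" until the informant has no more to name. After that, "The interview recording and generated transcription will be stored until the data capture form has been completed and will then be deleted". (Section 4.1 differs and keeps anonymised transcripts; the two should be reconciled.)

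The research team also delivers the intervention (section 1.2). In that arm the informant takes part in pre-meets and in "post-meets with key informants (and team) 1 week, 1 month and 3 months post-workshop to refine the CLD, identify further solutions". The trial is unblinded (sections 2.1 and 3.2). The main analysis is a linear regression of the policy count, adjusted for baseline (section 3.3).

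**The concern.** A policy enters the count only if the informant mentions it in answer to a question that already carries the DHI qualifier. That answer depends on what the informant takes to be aimed at dietary inequalities, and the protocol expects the intervention to alter exactly this. Research question 2 (section 1.3) asks how understanding of DHI and its solutions evolves over the intervention. Understanding is a secondary outcome (section 1.4.2), compared between arms in these same informants at baseline and 12 months (section 3.3). Shared understanding is also one of the theorised mechanisms (section 2.8.2).

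Two LAs with the same food actions in the window could therefore give different counts at 12 months, because one informant has spent months discussing local food work as DHI and the other has not. Part of the arm difference would then be a difference in reporting. A policy that is never mentioned leaves no record, so no later coding or analysis can restore it.

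**Working it through.** **1. Reproduce the plan's figures.** Inputs from section 3.1: 30 LAs per arm, a difference of 2 policies, SD 3 or SD 2, stated power 72% and 97%. The significance level is not stated; two-sided 5% is assumed. For a two-sample t-test the noncentrality is d / (SD × √(2/30)), with 58 degrees of freedom.

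- SD 3: standard error 3 × 0.2582 = 0.775; noncentrality 2/0.775 = 2.58; power 71.9%.
- SD 2: standard error 2 × 0.2582 = 0.516; noncentrality 2/0.516 = 3.87; power 96.8%.

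Both agree with the protocol, so the same formula is used below.

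**2. Spurious excess.** Suppose an LA has m in-window food actions that an informant might or might not name as DHI-directed, and exposure raises the share named by s. With no true effect, the expected arm difference is m × s. Neither input is in the protocol. Illustrations: 2 × 0.10 = 0.2; 2 × 0.25 = 0.5; 4 × 0.25 = 1.0.

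**3. Chance of a significant result with no true effect** (nominal 5%):

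| Assumed excess (policies) | SD 3 | SD 2 |
|---|---|---|
| 0.2 | 6% | 7% |
| 0.5 | 10% | 16% |
| 1.0 | 25% | 48% |

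The smallest observed difference that reaches significance, unadjusted, is 1.55 policies at SD 3 and 1.03 at SD 2.

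**4. Baseline adjustment.** The baseline answer is given before anyone is exposed, so it carries no information on a shift that follows randomisation in one arm. Adjustment reduces the residual SD and leaves the excess in place. With an assumed baseline correlation of 0.5 the SD is multiplied by √(1 − 0.25) = 0.866, and an excess of 1.0 policy becomes significant 31% (SD 3) or 59% (SD 2) of the time, against 25% and 48% unadjusted.

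**5. Safeguards already in the text.**

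- *Implementation dates* allow work that falls outside the window to be excluded. They do not help with actions inside the window that one arm names and the other does not. Question 4 gives no window at all.
- *Solution Bank prompts* make it less likely that an informant forgets an action that goes by another name. The post-meets, however, draw on what appears to be the same resource (section 1.2, reference 13), so intervention informants may already know the examples.
- *Common wording* is the same in both arms, but the informants' reading of it may not be.

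**The case against.** The strongest reply is that the protocol does not leave the decision to the informant. A researcher runs the interview, asks for detail on each policy and completes the form, and could screen entries against the definition. Coding rules are often left to an analysis plan or manual. This stands in part. A reader might infer that the informant's own label decides the count, but the protocol does not say who makes the final decision. It remains true that no rule is stated, and that screening can act only on what was mentioned. The wording of the question is fixed in this document, whatever a later plan says about coding.

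Second, a reader might infer that long-standing work could simply be renamed and appear as an effect. The dates in question 2 largely block that. What is left is actions planned or implemented inside the window.

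Third, section 2.8.3 says of control-arm events: "This will include gatherings like holiday hunger working group meetings, food programme meetings, and food poverty action plan workshops". It is tempting to read this as showing that control informants file such work under other names and would omit it. It does not. These are meetings to be observed, not policies, and they are chosen with the informant as relevant to DHI. If anything, they suggest that control informants can recognise such work as DHI-related.

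Fourth, counting explicitly DHI-directed policies is a legitimate choice of outcome, and a real change of aim in an existing policy is a genuine effect. Both points are accepted, and neither calls for a different outcome.

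**Conclusion.** The point holds as a risk of differential ascertainment in the primary outcome. The only stated application of the explicit-aim filter is a question to one unblinded informant whose understanding of DHI is meant to change in one arm. Dates and prompts reduce the risk but do not remove it.

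The size cannot be obtained from the protocol. At the low end of the assumed range the error rate hardly moves from 5%; at one policy, half the target difference, it is five to ten times nominal. The document favours neither end, so it does not support a claim that relabelling would produce a false positive, only that the design could not rule it out. That the intervention shifts the informants' answers is an inference from the protocol's own theory of change, not something it states. The figures also assume that the Table 1 guide, which is titled for baseline, is used at 12 months as well.

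**What to change.** Keep the primary outcome and change how it is collected.

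1. At both time points, open Table 1, question 1 by asking for all food- and diet-related policies planned or implemented in the window, before and without the DHI qualifier. For each, record the stated aim, target group and date. State one window: section 1.4.1 refers to the last 12 months, while question 1 also takes in the next 12.
2. Write a fixed rule for when an aim counts as explicit. Have existing team members apply it to the data capture forms with LA name, arm and, where possible, time point removed.
3. Report the count of all in-window food policies as a supportive analysis. A difference seen only in the DHI-filtered count may be relabelling or genuine retargeting and should be read with caution; it should not be taken as proof of relabelling. The unfiltered count may also be noisier. If its SD were 6 (an assumption), the noncentrality for two policies would be 2/(6 × 0.2582) = 1.29 and power about 25%, so a null result there would say little.

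The cost is a somewhat longer interview, a short coding rule and some coding time; no LAs or staff are added. Masking will be imperfect, because the descriptions still come from the informant. The change should be made before baseline interviews start, so that both time points use the same question.
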